### **1.c Randomization Method**

PAT sites will be randomly assigned to HEALTH or usual care via a dynamic randomization scheme, in which percent of low-income and number of families served will be considered so that we achieve similar distributions in both arms of the study. The first 12 sites will be randomized to HEALTH or usual care arms in a 1:1 ratio within five site pairs where two sites are matched closely on total size and percent of low-income families. There are two sites that cannot be matched; for these two sites, several possible randomizations will be elicited in a 1:1 ratio and the randomization that best maintains the overall balance (on total size and percent of low income families) between the two treatment groups will be selected. Subsequent sites will use a dynamic randomization scheme, the details of which will be determined when those sites are recruited. Again, they will be randomized to best maintain the overall balance (on total size and percent of low-income families) between the two treatment groups.

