## ***J3 Statistical Methods***

Initial analyses will use t-tests and chi-square tests to compare baseline characteristics across groups. If continuous variables do not satisfy the normality or equal variance assumptions of the t-tests, we will explore data transformations and, if appropriate transformations cannot be identified, may employ Wilcoxon's test.

The primary analysis outcome, weight change between visits, was compared between intervention groups using a linear mixed-effect model with repeated measures. The model included a fixed effect for intervention group, time point, and the intervention

---

by time point interaction with a random effect for participants nested within site. In addition, we may employ models that adjust for covariates (e.g., income), if these are not balanced by randomization. The covariance structure will be determined after evaluating correlation coefficients across time and assessing both Akaike's Information Criterion and Bayesian information Criterion.

Secondary continuous outcomes will be analyzed with the same mixed-effect model. If model assumptions of normality are violated, data will be rank-transformed prior to analysis. The secondary binary outcome will be assessed using a binomial generalized estimating equation (GEE) model repeated measures, while secondary ordinal outcome (physical activity category) will be analyzed using a multinomial GEE model with repeated measures. Due to the multiple comparisons, only the primary endpoint—weight change from baseline to 24 months—will be reported as an unadjusted comparison. All other p-values will be adjusted for multiple comparisons using the Benjamini-Hochberg linear step-up procedure to control the false discovery rate across comparisons. Participants with missing data for all outcomes after baseline were excluded. Participants with at least one follow-up measurement (i.e., 12-month, 24-month, or both) were included in the analyses.

Mixed-effect analyses will also be conducted for subgroups. A per protocol analysis will also be conducted for participants completing at least four home visits. Least squares means with 95% confidence intervals will be report for changes from baseline. No adjustment for multiplicity will be applied to the confidence interval widths.

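### The primary model leaves out the two site factors used to balance the randomisation; adjusting for them would give a small gain in precision at little cost

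*Combined protocol and SAP*

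**What the plan says.** Section 1.c (Randomization Method) allocates whole sites. Its stated aim is that "percent of low-income and number of families served will be considered so that we achieve similar distributions in both arms of the study". Among the first 12 sites there are five pairs matched on total size and percent low-income, and the two unmatched sites take whichever candidate randomisation gives the best balance. For the remaining sites a dynamic scheme applies, "the details of which will be determined when those sites are recruited", with the same goal: "they will be randomized to best maintain the overall balance (on total size and percent of low-income families) between the two treatment groups".

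Section J3 (Statistical Methods) says that the primary outcome, "weight change between visits, was compared between intervention groups using a linear mixed-effect model with repeated measures". The fixed effects it lists are group, visit and the product of the two. For clustering it gives only this: "with a random effect for participants nested within site". Neither balancing factor is listed. The only provision for adjustment is that "we may employ models that adjust for covariates (e.g., income), if these are not balanced by randomization". J3 carries the same specification to other outcomes: "Secondary continuous outcomes will be analyzed with the same mixed-effect model".

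**The concern.** When allocation is forced to balance a prognostic factor, the treatment estimate varies less over repeated randomisations, because that factor no longer contributes chance differences between arms. A model that omits the factor still counts its variance as noise. In a cluster trial that noise sits in the site variance, so the reported standard error exceeds the true one and the confidence interval is too wide.

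The adjustment clause in J3 does not cure this. It is discretionary, and it is triggered by imbalance, so it is least likely to apply to the two factors the allocation balances. Its example, income, is not said to mean the site's percent low-income. It also leaves the form of the primary model to a judgement made after balance has been seen.

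What is at stake is precision and prespecification. Validity is not.

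**Working it through.** **Inputs from J1.** Two-sided 0.05; difference 4 kg; SD 10 kg; ICC 0.01, 0.02 or 0.05; 7 completers per site; 19 sites per group in the power table; 20 per arm randomised.

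**Assumption.** The share of between-site variance explained by the two factors, R², is not in the documents. I take 0.1 to 0.5 and also show 0.

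**Plan's own table first.** Per arm, ignoring clustering, n = 2 × [10 × (1.960 + z)/4]², which is 98.1 for power 0.8 and 131.3 for 0.9. Setting 19m = n × [1 + (m − 1) × ICC] gives m = n(1 − ICC)/(19 − n × ICC):

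- power 0.8: 5.39 / 5.64 / 6.61, rounding up to 6 / 6 / 7
- power 0.9: 7.35 / 7.86 / 10.04, rounding up to 8 / 8 / 11

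All six cells of Table 2 are reproduced. With a t reference, 19 sites per group at ICC 0.05 give power 0.795, consistent with the stated 0.8. The table takes no credit for balancing, so the omission does not undercut it.

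**Effect of omitting the factors, 20 sites per arm.**

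- Reported variance: 2 × [100 × ICC + 100 × (1 − ICC)/7]/20
- True variance under full balance, and adjusted-model variance: the same with 100 × ICC × (1 − R²) in place of 100 × ICC

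Example, ICC 0.05 and R² 0.5: reported SE = √[2 × (5 + 13.571)/20] = 1.363; adjusted SE = √[2 × (2.5 + 13.571)/20] = 1.268; ratio 1.075. Power uses noncentral t with 38 df unadjusted and 36 df adjusted.

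| ICC | R² | SE reported | SE adjusted | Excess | Power gain (points) |
|---|---|---|---|---|---|
| 0.01 | 0.1 / 0.3 / 0.5 | 1.231 | 1.226 / 1.218 / 1.210 | 0.3 / 1.0 / 1.7% | 0.0 / 0.3 / 0.5 |
| 0.02 | 0.1 / 0.3 / 0.5 | 1.265 | 1.257 / 1.241 / 1.225 | 0.6 / 1.9 / 3.3% | 0.2 / 0.7 / 1.2 |
| 0.05 | 0.1 / 0.3 / 0.5 | 1.363 | 1.344 / 1.307 / 1.268 | 1.4 / 4.3 / 7.5% | 0.6 / 2.0 / 3.4 |

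At ICC 0.05, power unadjusted against adjusted is 0.819 vs 0.825, 0.826 vs 0.846 and 0.832 vs 0.867. The 95% CI half-width is 2.76 kg unadjusted against 2.73 / 2.65 / 2.57 kg. The unadjusted type I error is 0.047 / 0.041 / 0.036. At R² = 0, adjusting costs about 0.1 point (0.816 vs 0.815 at ICC 0.05).

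**Repeated-measures simulation.** 40 sites of 10 mothers, all with a 12-month change and 7 with a 24-month change. Assumed: 12-month SD 8, correlation 0.65 between visits, equal site effect at both visits, five matched pairs plus two sites, then 28 sites by minimisation with a 0.8 biased coin. REML with a site intercept; 3,000 replicates per cell (Monte Carlo SE about 0.006 for power). Adjusted means both factors crossed with time point.

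| ICC | R² | Power unadjusted | Power adjusted | Difference (points) |
|---|---|---|---|---|
| 0.05 | 0 / 0.1 / 0.3 / 0.5 | 0.861 / 0.857 / 0.865 / 0.875 | 0.855 / 0.860 / 0.885 / 0.903 | −0.6 / 0.3 / 2.0 / 2.8 |
| 0.02 | 0 / 0.3 / 0.5 | 0.907 / 0.904 / 0.908 | 0.899 / 0.907 / 0.920 | −0.8 / 0.3 / 1.2 |

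At ICC 0.05, type I error is 0.046 / 0.038 / 0.038 / 0.034 unadjusted against 0.047 / 0.041 / 0.044 / 0.045 adjusted.

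**Why cross the factors with time.** Suppose they enter as main effects only, and their 12-month effect is half the 24-month one. Over 12-month SDs of 6 to 10 and correlations of 0.5 to 0.8, only 58% to 94% of the explained 24-month variance is removed. The 3.4-point gain (ICC 0.05, R² 0.5) then falls to between 2.0 and 3.2.

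**Where the direction fails.** With no site term at ICC 0.05, type I error is 0.063 to 0.088. With one constant site intercept, and a 12-month site effect half that at 24 months (ICC 0.05, R² 0.3), mean SE is 1.178 against an empirical 1.260 and type I error is 0.062.

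**The case against.** The strongest objection is that the documents do not fix the direction. J3's random-effect wording can be read with or without a site intercept, and under two readings the standard error is too small. That stands as a condition on the conclusion, and it is a reason to state the random effects explicitly.

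The size is also uncertain. Nothing in the plan shows that site size or percent low-income predicts weight change, so R² could be near zero, and the largest figures pair the highest assumed R² with the highest planned ICC. The closed form assumes full balance, while the scheme for 28 of the 40 sites is still open. If half the chance-imbalance variance remained, the excess at ICC 0.05 would fall from 1.4 / 4.3 / 7.5% to 0.7 / 2.1 / 3.5%. These points shrink a gain that is already small.

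On cost, the simulated loss at R² = 0 (0.6 to 0.8 points) exceeds the simulated gain of 0.3 points at ICC 0.05 with R² 0.1 and at ICC 0.02 with R² 0.3. Differences this small are comparable with Monte Carlo error or below it. Over part of the range the change is therefore neutral for power, and the remaining benefit is prespecification.

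Parts of J3 are in the past tense. If the analysis had already been run, changing the primary model would be a post-data change. The tense alone does not establish that.

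**Conclusion.** The concern holds, as an optional improvement. The primary model omits both factors by which the sites are balanced, and the conditional clause does not bring them in. Provided the factors predict 24-month change and a site intercept captures the 24-month between-site variance, the reported standard error is too large by 0.3% to 7.5% over ICC 0.01 to 0.05 and R² 0.1 to 0.5, and adjusting gains about 0 to 3.4 points of power. The omission causes no bias and no type I inflation. The figures assume equal site sizes, and the closed form also assumes full balance on both factors. Confidence is medium, because R² and the exact random-effects structure are not given.

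**What to change.** In J3, prespecify number of families served and percent low-income as site-level covariates, each with its interaction with time point, in the primary mixed model and in the continuous secondary models that share it, regardless of observed balance. State the scale on which each enters. Specify a random intercept for site alongside participant within site, and say whether the site effect may differ between 12 and 24 months. For these two factors this replaces the optional clause.

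The cost is one or two sentences of SAP wording, with data already held for randomisation, and two site-level degrees of freedom (38 to 36). If the analysis has already been run, report the adjusted model as a sensitivity analysis instead.

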### **1.d Early Withdrawal of Participants**

**Mothers:** Participants who decide they would no longer like to participate in the study are free to withdraw at any time; they may continue with PAT visits, but will not be part of the study (will not participate in any study measures).

**PAT staff:** Participants who decide they would no longer like to participate in the study are free to withdraw at any time; this will not affect their employment, but they will not be part of the study (will not participate in any study measures).

### **1.e When and How to Withdraw Participants**

Should a participant (mother or PAT staff) wish to withdraw from the study, they can do so at any time by completing the withdrawal letter, found in the Participant section of the Human Research Protection Office website at <http://hrpo.wustl.edu> (or use this link: <https://hrpo.wustl.edu/participants/withdrawing-from-a-study/>) or requesting that the Investigator send a copy of the letter.

### **1.f Data Collection and Follow-up for Withdrawn Participants**

Participants (mother or PAT staff) who decide to withdraw will not participate in any additional measurement or follow-up.

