## **J Statistical Plan**

### ***J1 Sample Size Determination and Power***

We are confident the tabulated computations that led to our decision to randomize 40 sites (20 to each arm) are, if anything, conservative. Tabulations are based on weight at 24 months as the primary outcome and are for two-sided tests at the 0.05 significance level.

**Table 2:** Number of subjects required in each PAT site for two-sided tests at the 0.05 level of significance.

# PAT sites per group	Power	Between group difference	Intraclass correlation coefficient		
			0.01	0.02	0.05
19	0.8	4	6	6	7
	0.9	4	8	8	11

---

The table entries (Table 2, above) are the required sample size per cluster completing data collection for power values of .8 and .9; for ICC values of .01, .02, .and .05; for 19 PAT sites per group, and for between group differences of 4 between-group difference in the baseline to 24-month change in body weight that can be detected. Prior data from the HEALTH effectiveness trial found the standard deviation of the change in weight from baseline to 24 months was 8.3 kg. To be conservative, the computations assume an increased value of 10 for the standard deviation. The computations also assume 7 mother will complete 24 months of follow-up at each of 19 PAT sites. The number actually enrolled will be increased to 10 mothers (to account for a potential dropout rate of 30%) and 40 sites (20 per arm). Based on the above parameter assumptions, Table 3 indicates that to achieve a power of 0.8 with 19 PAT sites per group and an intraclass correlation coefficient as high as 0.05, the between-group difference in the change in weight from baseline to 24 months would have to be 4. Since the HEALTH study saw a 24-month decrease in weight of 1.5 (+/- 8.3) kg in the intervention group and a 24-month increase of 3.2 (+/-7.6) kg in the control, we are confident the target of 19 PAT sites per group with 7 mothers providing 24-month data is sufficient. We emphasize these computations are conservative because they allow for more variability (i.e., assume a larger standard deviation) than was observed in HEALTH, and because our analysis will add power by including data on the dropouts who do not provide 24-month data but who do provide data at 12 months.

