## ***J5 Missing Outcome Data***

Missing values will be examined carefully to determine their causes and potential impact on subsequent analyses. We will evaluate whether data are missing at random. For data that are missing at random, we will conduct some analyses involving mixed models. In these analyses, missing values are dealt with in a natural manner, in that existing values are analyzed, and no observations are deleted due to missing values. In addition, we will conduct analyses where we do multiple imputation of missing values in a way that biases towards the null. Finally, we will conduct sensitivity analyses which assume that data are missing at random, to see how this impacts our results. Loss to follow up and missing and incomplete data will be monitored closely by the DSMB, to solve potential issues of missing data before there is a substantial impact on the results. For data collected as responses to questionnaires, all forms will be reviewed for

---

completeness before the participant leaves the study visit. Data entry will be accomplished quickly so that missing values may still be retrieved.

Under intention-to-treat principles, all participants will be included in the analysis. Where appropriate, analyses involving mixed models may be used such that all existing values are analyzed, and no observations are deleted due to missing values. Sensitivity analyses under various assumptions regarding the missing data will be conducted to confirm the robustness of the results.

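### A mother who decides to withdraw is never weighed again, even if she stays in PAT, because sections 1.d to 1.f include no offer of a weight-only visit

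*Combined protocol and SAP*

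**What the plan says.** Section 1.d covers mothers who no longer want to be in the study. Of these it says "they may continue with PAT visits, but will not be part of the study", and it adds that they take part in no study measures. Section 1.f repeats that they "will not participate in any additional measurement or follow-up". Section 1.e gives the route, an institutional withdrawal letter. None of the three sections describes a reduced level of participation or a request for a final weight.

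Other sections bear on the point:

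- H2 schedules weight at baseline, 12 and 24 months.
- J1 allows for 30% dropout and counts on the 12-month weights of mothers who have no 24-month weight.
- J3 keeps anyone with at least one follow-up measurement and drops the rest: "Participants with missing data for all outcomes after baseline were excluded".
- J5 plans mixed models, multiple imputation that leans towards no effect, and sensitivity analyses.
- Appendix C already has remote weighing: by video call, by a photograph of the scale reading, or with a mailed scale as a fallback.

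**The concern.** The rule treats leaving the study's tasks and refusing to be weighed as one decision. They need not be. A mother who keeps her PAT visits remains in contact with the site, and one weighing asks less of her than the full set of surveys, waist and blood pressure measurements.

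What is at stake is the primary outcome. Mothers may leave because of how their weight is going. They may also leave for different reasons in the two arms, since only HEALTH sites bring weight and lifestyle content into the visits (section 2.c). If so, the missing weights are not a random subset. The planned models can adjust under assumptions about those weights, but they cannot check the assumptions. Observed weights from some of these mothers would.

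**Working it through.** **Inputs from J1.** Tabulations are for "two-sided tests at the 0.05 significance level". The difference is 4 kg, and "the computations assume an increased value of 10 for the standard deviation". There are 19 sites per arm with 7 completers each. Enrolment is raised to 10 mothers at each of 20 sites per arm for 30% dropout.

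**Reproducing the plan's figures.** The normal approximation with design effect 1 + (m − 1) × ICC gives the completers needed per site:

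m = n(1 − ICC) / (19 − n × ICC), with n = 2 × [10 × (1.960 + z_power) / 4]²

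For power 0.8, n = 98.1. At ICC 0.05, m = 98.1 × 0.95 / (19 − 4.91) = 6.61, rounded up to 7. Across ICC 0.01, 0.02 and 0.05 the results are 5.39, 5.64 and 6.61 for power 0.8, and 7.35, 7.86 and 10.04 for power 0.9. Rounded up, they are 6, 6, 7 and 8, 8, 11, which are all six entries of Table 2. The dropout step also agrees: 7 / 0.70 = 10.

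**Power with the full planned loss** (4 kg, SD 10, ICC 0.05, m = 7, design effect 1.30):

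- 19 sites per arm: effective n = 133 / 1.30 = 102.3 per arm, SE = 10 × √(2 / 102.3) = 1.398, power = Φ(4 / 1.398 − 1.960) = 0.816.
- 20 sites per arm: effective n = 140 / 1.30 = 107.7, SE = 1.363, power = 0.835.
- With a t reference on 2(k − 1) degrees of freedom, where k is sites per arm, the values are 0.795 and 0.816.

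**What a weight-only offer could regain.** Planned losses are 400 × 0.30 = 120, from all causes. Let w be the share of these that are formal withdrawals, and f the share of withdrawing mothers who accept a 24-month weighing. The documents give neither, so both are assumed. Weights regained = 120 × w × f, and completers per site = 7 + 3 × w × f. Power is for 20 sites per arm, ICC 0.05, normal approximation.

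| w | f | Weights regained | Completers per site | Power |
|---|---|---|---|---|
| none | none | 0 | 7 | 0.835 |
| 10% | 25% | 3 | 7.075 | 0.838 |
| 10% | 50% | 6 | 7.15 | 0.841 |
| 25% | 50% | 15 | 7.375 | 0.849 |
| 50% | 50% | 30 | 7.75 | 0.861 |
| 100% | 100% | 120 (ceiling) | 10 | 0.913 |

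**Bias, as illustration only.** Suppose completers show 4 kg and all 120 lost mothers had no benefit. The effect over everyone would be 0.7 × 4 + 0.3 × 0 = 2.8 kg. Adding 30 zero-effect weights to the 280 completers would move the observed effect to 280 × 4 / 310 = 3.6 kg. Adding 3 would move it to 280 × 4 / 283 = 3.96 kg. The offer would therefore close only part of such a gap.

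**The case against.** The strongest reply is that withdrawal here means leaving the study, not stopping the intervention. No section treats missed or ended PAT or HEALTH visits as withdrawal, so the common fault of ending follow-up when treatment stops does not arise. What a withdrawing mother gives up is mainly the study measures, and that she would accept one more is conjecture. This stands: the documents do not show that the weights are lost needlessly. It does not answer the point that she is never asked.

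Several stronger readings are tempting but not supported:

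- *Every withdrawal ends measurement.* Section 1.f covers those who decide to withdraw. Section I2 also withdraws mothers who become pregnant, without saying whether measurement continues.
- *A mother tired of recordings or surveys must leave.* H2 makes recording subject to her consent, and no section says that declining a survey counts as withdrawal.
- *The trial is short of power.* It is not under the method that reproduces Table 2. The 0.795 comes from a t reference and 19 sites per arm; with the 20 planned, that reference gives 0.816.
- *All 120 losses could be recovered by this route.* The 30% covers every kind of dropout.
- *The rule breaks intention to treat.* J5 states "Under intention-to-treat principles, all participants will be included in the analysis", while J3 drops mothers with no follow-up outcome. That conflict is real but separate: it affects any mother without follow-up data, section 1.f did not create it, and this change would not remove it.

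Two more points count on the other side. A 12-month weight already taken stays in the analysis, and J5's imputation and sensitivity analyses address informative loss in part. Also, the withdrawal letter and the consent pages are not in the text available for review, so whether either offers partial withdrawal is unknown.

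**Conclusion.** The point holds as a limited one. Sections 1.d to 1.f state a rule: a mother who decides to withdraw has no further measurement, even if she stays in PAT, and they provide no step to ask for a weight. A mother who leaves after month 12 loses her 24-month weight. One who leaves before month 12 contributes no follow-up weight at all.

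The yield is about 3 to 30 weights at 24 months, if 10% to 50% of the 120 planned losses are formal withdrawals and 25% to 50% of those mothers accept. The matching power gain, from 0.835 to at most 0.861 in that range, is small and not needed to reach 0.80 under the plan's own calculation. The case therefore rests on bias, if withdrawal is related to weight or to arm. The documents give no withdrawal rate and no reasons by arm, so the size of that bias cannot be estimated. The 2.8 kg figure is an extreme illustration, not an estimate. The change is still worth making, because it is voluntary, can only add primary-outcome data, and uses visits and remote weighing the trial already has.

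**What to change.** Amend sections 1.d to 1.f as follows:

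- When a mother says she wants to withdraw, offer her weight-only participation at 12 and 24 months, voluntarily and with her consent, in person or by the remote scale procedure in Appendix C.
- Stop all measurement only if she declines.
- Record the level of withdrawal chosen and the reason, and report both by arm.
- State whether the section applies to mothers withdrawn under I2.

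The cost is IRB approval of the wording, some administrative work, and the usual visit payment: $20 (L2) or $30 (Appendix C) per visit. That is at most 2 × $30 = $60 per mother, or 30 × $60 = $1,800 if 30 mothers accepted both visits. Data collectors' time is extra and not costed in the documents. The withdrawal letter appears to be an institutional form, so the offer may fit better in the study's own consent information and staff script.
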